### **4.4.3 Correlation between regulation and outcomes for patients who provided data for at least two feedback sessions (CRED-nf 6b)**

A linear model will be used with the number of OBEs at post-assessment as the dependent variable, the value at T0 as covariate and mean proportion of successful trials across all sessions as the variable of interest.

## **4.5 Interim analyses**

No interim analyses were planned or performed.

## 5 Safety

Adverse events (AEs) and Serious Adverse Events (SAEs) as well as PHQ-15 were collected during the therapy sessions and will be listed by therapy arm. For PHQ-15, the raw data will be presented in graphical form per randomization arm and point in time.

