### 3.5 Premature termination of the trial

#### 3.5.1 Termination of the trial

The responsible investigator has the right to discontinue the trial

- if information emerges that affects the benefit/risk ratio of the trial;
- if actual recruitment and follow-up rates do not guarantee the necessary statistical power;
- if there are repeated serious adverse events (SAE) presumably associated with the trial.

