### 6.1.2 Documentation of adverse events (AE)

AEs will be documented at the AE form including the following information: start, end, description, date, intensity, causality, and consequence. The documentation of AEs will be realized for all intervention arms including the delayed treatment group during the study (from study inclusion to last follow-up visit).

Inpatient treatment of comorbidities, for example, a massive worsening of psychiatric symptoms, must be classified as SAEs and documented in the AE form.

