### 6.1.3 Documentation of serious adverse events (SAE)

SAEs will be documented in the AE form, which contains additional questions for SAEs. At first, the original form remains at the study center. After the end of treatment (week 8 or 16, respectively) and

follow-up visit (month 6), the original AE form will be sent to the ZKS data management or handed to the monitoring staff together with all other case report forms. If additional information to the SAE are available at a later time point, they will be documented as well and sent to the ZKS data management or monitoring staff, respectively. SAEs will be documented during the patient's study period (from study inclusion to last follow-up visit). SAE involving patient's death will be immediately reported to the principal investigator. The study team will provide additional required information upon request. Confidentiality of patients' data will be protected by a documentation system working with anonymous patient codes. The primary notification as well as all following notifications of SAEs must be assignable to each other via the patient's identification number.

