## **6.3 Safety analyses**

Every patient will be monitored closely regarding safety during the course of the study and includes the assessment of AEs and SAEs at the end of treatment (t1) and follow-up (t2). All AEs and SAEs will be analyzed descriptively in the final analysis.

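### SAP section 5 takes adverse events from therapy sessions, contrary to protocol 6.1.2, 6.1.3 and 6.3; the waiting period and follow-up have no scheduled enquiry, and the listing has no split by exposure

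*SAP*

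**What the plan says.** On the source and layout of the safety data, SAP section 5 states that AEs and SAEs "were collected during the therapy sessions and will be listed by therapy arm". The next sentence plots PHQ-15 by randomisation arm. Neither term is defined there.

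Protocol 6.1.2 sets a wider window. AEs are to be documented "for all intervention arms including the delayed treatment group during the study (from study inclusion to last follow-up visit". Protocol 6.1.3 sets the same window for serious events: "SAEs will be documented during the patient's study period (from study inclusion to last follow-up visit". Protocol 6.3 says that safety monitoring "includes the assessment of AEs and SAEs at the end of treatment (t1) and follow-up (t2", and adds: "All AEs and SAEs will be analyzed descriptively in the final analysis".

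The operational schedule is closer to the SAP. In the flow chart, the AE row is marked weekly during therapy and at t1, and is blank at the waitlist's week-8 visit and at t2. In protocol 5.4 and 5.5, AEs appear only in the weekly on-treatment list, which covers weeks 1–7 in the active arms and weeks 9–15 in the delayed arm. They do not appear in the lists for waitlist week 8, t1 or t2.

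On SAE forms, protocol 6.1.3 says: "At first, the original form remains at the study center". The form goes to data management or the monitor after end of treatment (week 8 or 16) and after the month-6 visit. Immediate reporting, to the principal investigator, is stated only for deaths. Protocol 3.5.1 lets the responsible investigator stop the trial "if there are repeated serious adverse events (SAE) presumably associated with the trial". Protocol 10.3 provides no independent safety committee.

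**The concern.** The protocol's safety text and its schedule disagree, and the SAP follows the narrower of the two. The gap falls unevenly. In the randomised 8-week period the active arms attend sessions at which AEs are asked about, while the waitlist attends none, and its comparison visit carries no AE item. Events in a listing by arm would then differ partly because one arm was asked and the other was not.

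Attribution is a second difficulty. SAP 2.2 recognises that the waitlist received fNIRS after T0WL, and so limits three-arm efficacy comparisons to T0 and T1/T0WL. Section 5 makes no such split for safety. Depending on what therapy arm means, events under delayed fNIRS could appear under the waitlist label, or immediate and delayed fNIRS could be pooled and the waiting period drop out of view.

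The third matter is separate from the listing. The protocol names repeated SAEs as a ground for ending the trial, but has no stated route by which non-fatal SAEs promptly reach those who would apply it.

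**Working it through.** The plan gives no figure to reproduce for this point. The check sets the documents side by side and then counts nominal observation time.

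**Scheduled AE enquiry, by source**

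| Period or visit | Protocol 6.1.2 / 6.1.3 / 6.3 | Flow chart | Lists in 5.4 / 5.5 | SAP 5 |
|---|---|---|---|---|
| Therapy sessions, all arms | yes | yes | yes | yes |
| t1 | yes | yes | not listed | not mentioned |
| Waitlist weeks 0–8, including T0WL | yes | no | not listed | no sessions held |
| Follow-up, including t2 | yes | no | not listed | no sessions held |

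**Inputs.** 26 patients per arm (synopsis); 8 weeks of therapy and an 8-week wait (protocol 1.2.1); 6 months of follow-up after end of treatment (protocol 5.5). Assumptions: 6 months is taken as 26 weeks, nobody drops out, and visit windows are ignored.

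**Nominal patient-weeks, inclusion to last follow-up**

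- Active arms: 8 + 26 = 34 weeks each, so 2 × 26 × 34 = 1,768.
- Waitlist arm: 8 + 8 + 26 = 42 weeks, so 26 × 42 = 1,092.
- Total: 1,768 + 1,092 = 2,860.

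**Split by type of period**

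- Therapy: 3 × 26 × 8 = 624, which is 624 / 2,860 = 21.8%.
- Waitlist untreated: 26 × 8 = 208, which is 208 / 2,860 = 7.3%.
- Follow-up: 3 × 26 × 26 = 2,028, which is 2,028 / 2,860 = 70.9%.
- Check: 624 + 208 + 2,028 = 2,860.

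**Randomised weeks 0–8 alone.** All arms: 3 × 26 × 8 = 624. Waitlist share: 208 / 624 = one third, with no scheduled enquiry.

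**Attribution.** Patients exposed to fNIRS: 26 immediate plus at most 26 delayed = 52. Share randomised to waitlist: at most 26 / 52 = 50%.

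**SAE notice.** Protocol 12.1 has serious protocol violations reported immediately to the principal investigator. Protocol 6.1.3 has deaths reported immediately to the same person. No corresponding sentence covers non-fatal SAEs.

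**The case against.** The strongest reply is that the protocol does require these data. Sections 6.1.2, 6.1.3 and 6.3 are explicit, and 6.1.2 names the delayed group. A reader might infer from SAP 5 that no safety data exist for the waiting period or follow-up. The documents do not support that. The schedules are plainly not exhaustive: the t1 list omits AEs although the flow chart marks them, and the t2 list includes comorbidities and medication although the flow chart leaves both blank. Comorbidities and medication are recorded at waitlist week 8 and, by 5.5, at t2. The AE form records start and end, so an earlier event can be dated if it is reported later. All of this stands. What remains is that unscheduled recall does not match weekly enquiry, and that SAP 5 describes session data only.

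A reader might also infer that delayed-fNIRS events will be misfiled as waitlist events. That depends on the label. If therapy arm means therapy received, they fall under fNIRS; the contrast with randomisation arm in the next sentence may point that way. The fair criticism is that the term is undefined and no period is given under either meaning.

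Nor is a planned safety comparison lost. The synopsis, 6.3 and 7.5.1 promise descriptive reporting only.

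Finally, a reader might infer that SAE information is withheld from the person who decides on stopping. For an SAE in week 1, the form would be sent about 8 − 1 = 7 weeks later in an active arm and 16 − 1 = 15 weeks later in the waitlist arm. That concerns the original form. The trial has a single centre, the stopping decision lies with the responsible investigator, and 5.6.1 has that investigator decide on discontinuation for AEs or SAEs after contacting the coordinating investigator. Protocol 9.2 also has the eCRF completed shortly after each visit, without saying whether this includes the AE form. The documents therefore do not show an uninformed investigator, only that no rule ensures prompt notice.

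**Conclusion.** The concern holds as an unreconciled contradiction with a practical consequence. SAP 5 and the assessment schedule are narrower than protocol 6.1.2, 6.1.3 and 6.3. If the schedule was followed as written, 208 of 624 nominal patient-weeks in the randomised period, all in the control arm, had no scheduled AE enquiry, and neither did the 2,028 follow-up patient-weeks. A listing by arm would then be asymmetric. Up to 26 of 52 fNIRS-exposed patients could have events shown under the wrong exposure; this upper bound assumes that every waitlist patient started fNIRS and that the label means randomised arm.

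The counts are nominal and measure time without a scheduled enquiry; they are not estimates of missed events. The documents do not establish that no events were recorded in these periods, that events will in fact be misattributed, or that SAEs were unknown to the investigator. The point affects the descriptive safety report and leaves the primary analysis untouched. It should be fixed before the safety tables are produced.

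**What to change.** **SAP 5.** List all AEs and SAEs recorded from inclusion to last follow-up, by randomised arm and exposure period: EEG; immediate fNIRS; waitlist weeks 0–8; delayed fNIRS; follow-up. Give patients and person-weeks as denominators, computed from actual dates because visits have windows. Replace or define therapy arm. State which periods had no active enquiry.

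**Schedule.** If collection is still open, add the existing AE form to the T0WL and t2 visits so that the flow chart and the visit lists match 6.1.2 and 6.3, and list it at t1 in 5.4. If collection is complete, re-tabulate what was recorded and state the limitation.

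**SAE notice.** Reconcile protocol 6.1.3 with 3.5.1, so that the text says how and when non-fatal SAEs reach those who apply the termination ground. The content of that rule is for the sponsor and the investigator to set.

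**Cost.** Table shells, some protocol wording, and one existing form at two existing visits. If data collection has ended, one re-tabulation and a limitation statement.

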## 6 Appendix

### 6.1 Abbreviations

AE	Adverse event
BMI	Body mass index
CONSORT	Consolidated Standards of Reporting Trials
OBE	Objective binge-eating episode
SAE	Serious adverse event

### 6.2 Code for EDE-Q

The EDE-Q instrument was introduced by Fairburn and Beglin (1994) and the scoring of the German version follows Hilbert and Tuschen-Caffier (2016).

```
scoring_edeq <- function(data, items = 1:22, keep = TRUE, nvalid = list(
  restraint = 3,
  eating_concern = 3,
  weight_concern = 3,
  shape_concern = 4
), digits = NULL) {
  if (min(data[, items], na.rm = T) < 0) {
    stop("Minimum possible value for EDE-Q items is 0")
  } else if (max(data[, items], na.rm = T) > 6) {
    stop("Maximum possible value for EDE-Q items is 6")
  }
  # check for number of specified items
  if (length(items) != 22) {
    stop("Number of items must be 22!")
  }
  items.restraint <- items[1:5]
  items.eating_concern <- items[c(7,9,13,14,15)]
  items.weight_concern <- items[c(8,12,16,18,19)]
  items.shape_concern <- items[c(6,8,10,11,17,20:22)]
  data <- data %>%
    mutate(
      nvalid.edeq.restraint = rowSums(!is.na(select(., all_of(items.restraint)))),
      score.edeq.restraint = rowMeans(select(., all_of(items.restraint)), na.rm = TRUE),
      score.edeq.restraint = ifelse(nvalid.edeq.restraint >= nvalid[['restraint']],
score.edeq.restraint, NA),
      nvalid.edeq.eating_concern = rowSums(!is.na(select(., all_of(items.eating_concern)))),
      score.edeq.eating_concern = rowMeans(select(., all_of(items.eating_concern)), na.rm =
TRUE),
      score.edeq.eating_concern = ifelse(nvalid.edeq.eating_concern >=
nvalid[['eating_concern']], score.edeq.eating_concern, NA),
      nvalid.edeq.weight_concern = rowSums(!is.na(select(., all_of(items.weight_concern)))),
      score.edeq.weight_concern = rowMeans(select(., all_of(items.weight_concern)), na.rm =
TRUE),
      score.edeq.weight_concern = ifelse(nvalid.edeq.weight_concern >=
nvalid[['weight_concern']], score.edeq.weight_concern, NA),
      nvalid.edeq.shape_concern = rowSums(!is.na(select(., all_of(items.shape_concern)))),
      score.edeq.shape_concern = rowMeans(select(., all_of(items.shape_concern)), na.rm =
TRUE),
      score.edeq.shape_concern = ifelse(nvalid.edeq.shape_concern >= nvalid[['shape_concern']],
score.edeq.shape_concern, NA),
      score.edeq.sum = rowMeans(cbind(score.edeq.restraint, score.edeq.eating_concern,
score.edeq.weight_concern, score.edeq.shape_concern), na.rm=TRUE),
      score.edeq.sum = ifelse(rowSums(is.na(cbind(score.edeq.restraint,
score.edeq.eating_concern, score.edeq.weight_concern, score.edeq.shape_concern)))<=1,
score.edeq.sum, NA)
    )
  }
}
```

```

)
# Keep single items and nvalid variables
if (keep == FALSE) {
  data <- data %>% select(-all_of(items), -starts_with('nvalid.'))
} else {
  data <- data
}
# Rounding
if (is.numeric(digits) == TRUE) {
  data <- data %>% mutate_at(vars(starts_with('score')), list(~ round(., digits)))
} else {
  data <- data
}
}
data
}

```

### 6.3 Code for determining the GSES score

The source for determining the score is (Schwarzer 1999)

```

function (data, items = 1:10, keep = TRUE, nvalid = 7, digits = NULL)
{
  library(dplyr, warn.conflicts = FALSE)
  if (min(data[, items], na.rm = T) < 1) {
    stop("Minimum possible value for GSES items is 1")
  }
  else if (max(data[, items], na.rm = T) > 4) {
    stop("Maximum possible value for GSES items is 4")
  }
  if (length(items) != 10) {
    stop("Number of items must be 10!")
  }
  items <- items
  data <- data %>%
    mutate(nvalid.gses = rowSums(!is.na(select(., items))),
           mean.temp = round(rowSums(select(., items), na.rm = TRUE)/nvalid.gses)) %>%
    mutate_at(vars(items), list(~ifelse(is.na(.), mean.temp, .))) %>%
    mutate(score.temp = rowSums(select(., items), na.rm = TRUE),
           score.gses = ifelse(nvalid.gses >= nvalid, score.temp, NA)) %>%
    select(-mean.temp, -score.temp)
  data
  if (keep == FALSE) {
    data <- data %>% select(-items, -nvalid.gses)
  }
  else {
    data <- data
  }
  if (is.numeric(digits) == TRUE) {
    data <- data %>% mutate_at(vars(score.gses), list(~round(., digits)))
  }
  else {
    data <- data
  }
  data
}
}

```

### 6.4 Code for determining the BIS/BAS score

The questionnaire was originally derived by Carver and White (1994) and is described on the website <https://local.psy.miami.edu/people/faculty/ccarver/availbale-self-report-instruments/bisbas-scales/>. The German version works with means (instead of sums) and only two subscales (Strobel et al. 2001), though more recent articles suggest other choices (Müller et al. 2013), but conclude that due to limited evidence, one retain the two factors.

```

scoring_bisbas_german <- function(data, items = 1:24, keep = TRUE,
                                nvalid = list(
                                  bis = 6,
                                  bas = 10
                                ),

```

```

      digits = NULL) {

if (min(data[, items], na.rm = T) < 1) {
  stop("Minimum possible value for BISBAS items is 1")
} else if (max(data[, items], na.rm = T) > 4) {
  stop("Maximum possible value for BISBAS items is 4")
}
# check for number of specified items
if (length(items) != 24) {
  stop("Number of items must be 24!")
}
items.rev <- items[c(1,3:21,23,24)]
items.bis <- items[c(2,8,13,16,19,22,24)]
items.bas <- items[c(3,4,5,7,9,10,12,14,15,18,20,21,23)]
data <- data %>%
  mutate_at(vars(all_of(items.rev)), list(~ 5 - .)) %>%
  mutate(
    nvalid.bisbas.bis = rowSums(!is.na(select(., all_of(items.bis)))),
    nvalid.bisbas.bas = rowSums(!is.na(select(., all_of(items.bas)))),
    score.bisbas.bis = rowMeans(select(., all_of(items.bis)), na.rm = TRUE),
    score.bisbas.bis = ifelse(nvalid.bisbas.bis >= nvalid[['bis']], score.bisbas.bis, NA),
    score.bisbas.bas = rowMeans(select(., all_of(items.bas)), na.rm = TRUE),
    score.bisbas.bas = ifelse(nvalid.bisbas.bas >= nvalid[['bas']], score.bisbas.bas, NA),
  )
# keep/discard original items and nvalid vars
if (keep == FALSE) {
  data <- data %>% select(-all_of(items), -starts_with('nvalid.'))
} else {
  data <- data
}
# Rounding
if (is.numeric(digits) == TRUE) {
  data <- data %>% mutate_at(vars(starts_with('score')), list(~ round(., digits)))
} else {
  data <- data
}

data
}

```

## 6.5 Code for determining the CERQ score

The questionnaire is derived and described in Garnefski et al. (2001) and a manual provided in Garnefski and Kraaij, V. Spinhoven, P. (2002). The shortened German version is described in G6rger et al. (2015). Originally, one missing item out of four per sub-score was allowed, but since the German version has only three items per sub-score, we do not permit any missing items.

```

scoring_cerq_german <- function(data, items = 1:27, keep = TRUE,
                                digits = NULL) {

if (min(data[, items], na.rm = T) < 1) {
  stop("Minimum possible value for BISBAS items is 1")
} else if (max(data[, items], na.rm = T) > 5) {
  stop("Maximum possible value for BISBAS items is 5")
}
# check for number of specified items
if (length(items) != 27) {
  stop("Number of items must be 27!")
}
items.self_blame <- items[0:2*9+1]
items.acceptance <- items[0:2*9+2]
items.rumination <- items[0:2*9+3]
items.positive_refocusing <- items[0:2*9+4]
items.refocus_planning <- items[0:2*9+5]
items.reappraisal <- items[0:2*9+6]
items.perspective <- items[0:2*9+7]
items.catastrophizing <- items[0:2*9+8]
items.blaming_others <- items[0:2*9+9]
data <- data %>%
  mutate(
    nvalid.cerq.self_blame = rowSums(!is.na(select(., all_of(items.self_blame))),

```

```

    score.cerq.self_blame = rowSums(select(., all_of(items.self_blame)), na.rm = FALSE),
    nvalid.cerq.acceptance = rowSums(!is.na(select(., all_of(items.acceptance)))),
    score.cerq.acceptance = rowSums(select(., all_of(items.acceptance)), na.rm = FALSE),
    nvalid.cerq.rumination = rowSums(!is.na(select(., all_of(items.rumination)))),
    score.cerq.rumination = rowSums(select(., all_of(items.rumination)), na.rm = FALSE),
    nvalid.cerq.positive_refocusing = rowSums(!is.na(select(.,
all_of(items.positive_refocusing)))),
    score.cerq.positive_refocusing = rowSums(select(., all_of(items.positive_refocusing)),
na.rm = FALSE),
    nvalid.cerq.refocus_planning = rowSums(!is.na(select(.,
all_of(items.refocus_planning)))),
    score.cerq.refocus_planning = rowSums(select(., all_of(items.refocus_planning)), na.rm =
FALSE),
    nvalid.cerq.reappraisal = rowSums(!is.na(select(., all_of(items.reappraisal)))),
    score.cerq.reappraisal = rowSums(select(., all_of(items.reappraisal)), na.rm = FALSE),
    nvalid.cerq.perspective = rowSums(!is.na(select(., all_of(items.perspective)))),
    score.cerq.perspective = rowSums(select(., all_of(items.perspective)), na.rm = FALSE),
    nvalid.cerq.catastrophizing = rowSums(!is.na(select(., all_of(items.catastrophizing)))),
    score.cerq.catastrophizing = rowSums(select(., all_of(items.catastrophizing)), na.rm =
FALSE),
    nvalid.cerq.blaming_others = rowSums(!is.na(select(., all_of(items.blaming_others)))),
    score.cerq.blaming_others = rowSums(select(., all_of(items.blaming_others)), na.rm =
FALSE)
  )
  # keep/discard original items and nvalid vars
  if (keep == FALSE) {
    data <- data %>% select(-all_of(items), -starts_with('nvalid.'))
  } else {
    data <- data
  }
  # Rounding
  if (is.numeric(digits) == TRUE) {
    data <- data %>% mutate_at(vars(starts_with('score')), list(~ round(., digits)))
  } else {
    data <- data
  }
  data
}

```

## 6.6 Code for determining the DERS score

The questionnaire is derived and described in Gratz and Roemer (2004), but for the correct order of variables and re-poling, please see

```

scoring_ders <- function(data, items = 1:36, keep = TRUE,
                        nvalid = list(
                          nonacceptance = 5,
                          goals = 4,
                          impulse = 5,
                          awareness = 5,
                          strategies = 6,
                          clarity = 4
                        ),
                        digits = NULL) {
  if (min(data[, items], na.rm = T) < 1) {
    stop("Minimum possible value for BISBAS items is 1")
  } else if (max(data[, items], na.rm = T) > 5) {
    stop("Maximum possible value for BISBAS items is 5")
  }
  # check for number of specified items
  if (length(items) != 36) {
    stop("Number of items must be 36!")
  }
  items.rev <- items[c(1, 2, 6, 7, 8, 10, 17, 20, 22, 24, 34)]
  items.nonacceptance <- items[c(11, 12, 21, 23, 25, 29)]
  items.goals <- items[c(13, 18, 20, 26, 33)]
  items.impulse <- items[c(3, 14, 19, 24, 27, 32)]
  items.awareness <- items[c(2, 6, 8, 10, 17, 34)]
  items.strategies <- items[c(15, 16, 22, 28, 30, 31, 35, 36)]
  items.clarity <- items[c(1, 4, 5, 7, 9)]
  data <- data %>%
    mutate_at(vars(all_of(items.rev)), list(~ 6 - .)) %>%
    mutate(

```

```

nvalid.ders.nonacceptance = rowSums(!is.na(select(., all_of(items.nonacceptance)))),
nvalid.ders.goals = rowSums(!is.na(select(., all_of(items.goals)))),
nvalid.ders.impulse = rowSums(!is.na(select(., all_of(items.impulse)))),
nvalid.ders.awareness = rowSums(!is.na(select(., all_of(items.awareness)))),
nvalid.ders.strategies = rowSums(!is.na(select(., all_of(items.strategies)))),
nvalid.ders.clarity = rowSums(!is.na(select(., all_of(items.clarity)))),
score.ders.nonacceptance = 6*rowMeans(select(., all_of(items.nonacceptance)), na.rm =
TRUE),
score.ders.nonacceptance = ifelse(nvalid.ders.nonacceptance >= nvalid[['nonacceptance']],
score.ders.nonacceptance, NA),
score.ders.goals = 5*rowMeans(select(., all_of(items.goals)), na.rm = TRUE),
score.ders.goals = ifelse(nvalid.ders.goals >= nvalid[['goals']], score.ders.goals, NA),
score.ders.impulse = 6*rowMeans(select(., all_of(items.impulse)), na.rm = TRUE),
score.ders.impulse = ifelse(nvalid.ders.impulse >= nvalid[['impulse']],
score.ders.impulse, NA),
score.ders.awareness = 6*rowMeans(select(., all_of(items.awareness)), na.rm = TRUE),
score.ders.awareness = ifelse(nvalid.ders.awareness >= nvalid[['awareness']],
score.ders.awareness, NA),
score.ders.strategies = 8*rowMeans(select(., all_of(items.strategies)), na.rm = TRUE),
score.ders.strategies = ifelse(nvalid.ders.strategies >= nvalid[['strategies']],
score.ders.strategies, NA),
score.ders.clarity = 5*rowMeans(select(., all_of(items.clarity)), na.rm = TRUE),
score.ders.clarity = ifelse(nvalid.ders.clarity >= nvalid[['clarity']],
score.ders.clarity, NA),
)
